##### **14.2.2 Assessment of Attribution**

The following definitions will be used to determine the causality (attribution) of the event to the study agent or study procedure.

- **Unrelated** – The event is clearly related to other factors such as the participant's clinical state, other therapeutic interventions, or concomitant medications administered to the participant.
- **Unlikely** – The event is doubtfully related to the investigational agent(s). The event was most likely related to other factors such as the participant's clinical state, other therapeutic interventions, or concomitant drugs.
- **Possible** – The event follows a reasonable temporal sequence from the time of drug administration, but could have been produced by other factors such as the participant's clinical state, other therapeutic interventions, or concomitant drugs.

- **Probable** – The event follows a reasonable temporal sequence from the time of drug administration, and follows a known response pattern to the study drug. The event cannot be reasonably explained by other factors such as the participant's clinical state, therapeutic interventions, or concomitant drugs.
- **Definite** – The event follows a reasonable temporal sequence from the time of drug administration, follows a known response pattern to the study drug, cannot be reasonably explained by other factors such as the participant's condition, therapeutic interventions, or concomitant drugs, AND occurs immediately following study drug administration, improves upon stopping the drug, or reappears on re-exposure.

#### 14.2.3 Assessment of Expectedness

The following definitions will be used to determine the expectedness of the event:

- **Unexpected** – An adverse event is unexpected if it is not listed in the investigator's brochure and/or package insert; is not listed at the specificity or severity that has been observed; is not consistent with the risk information described in the protocol and/or consent; is not an expected natural progression of any underlying disease, disorder, condition, or predisposed risk factor of the research participant experiencing the adverse event. \*Modified from [21 CFR 312.32 \(a\)](#)
- **Expected** – An adverse event is expected if it does not meet the criteria for an unexpected event, OR is an expected natural progression of any underlying disease, disorder, condition, or predisposed risk factor of the research participant experiencing the adverse event.

### 14.3 Reporting of Adverse Events

#### 14.3.1 Routine Reporting of Non-Serious Adverse Events by Site Investigators

Routine AE recording will occur via data entry into the study eCRF. Recording of adverse events will begin once the patient is consented and will continue until 30 days after the last dose of protocol therapy. Adverse events will be monitored by the Protocol Management Team (PMT). Adverse events that do not meet the criteria of serious OR are not unanticipated problems do not require expedited reporting. AEs reported through expedited processes (i.e. reported to the IRB, DSMC, FDA, etc.) must also be reported in routine study data submissions.

#### 14.3.2 Expedited Reporting Requirements of SAEs and UPs by Site Investigators

##### 14.3.2.1 *Criteria for Reporting SAEs/UPs to the Coordinating Center*

Serious Adverse Events meeting the criteria specified below will be reported to the Coordinating Center within 24 hours of notification that the event occurred.

Adverse events that require expedited reporting include:

- AEs or SAEs that meet the definition of an unanticipated problem
- AEs associated with
  - TLS ([Section 14.5](#))
  - overdose ([Section 14.6](#)), suspected abuse/ misuse,

- pregnancies ([Section 14.7](#))
- All deaths that occur within 30 days of active treatment
- All deaths that occur after 30 days of active treatment that are unexpected and possibly, probably, or definitely related to the study agent or procedure
- All serious adverse events, regardless of relationship to study agent or study procedure, that occur within 30 days of the last day of treatment
- All serious adverse events that occurred after 30 days of active treatment/therapy that are considered possibly, probably, or definitely related to the study agent or procedure

Note: Follow-up reports must be submitted for all events that require expedited reporting when the status of the event changes and until the resolution or stabilization of the event.

Reportable serious adverse events must be followed until the event is resolved, stabilized, or determined to be irreversible by the participating investigator; for ongoing reportable adverse events that are unrelated to study agent, the follow-up period may end at the 30-days post study-drug assessment. The Coordinating Center should be consulted prior to ending the follow-up of events that have stabilized.

#### *14.3.2.2 Non-COH Sites: Procedure for Reporting SAEs/UPs to the COH Data Coordinating Center*

1. Sites are to report to their local IRB per their site's specific institutional and IRB guidelines. As soon as possible, non-COH sites will provide to the COH Data Coordinating Center copies of the IRB submission and corresponding IRB response.
2. Document/describe the SAE/UP on each of the following:
  - a. MedWatch 3500A
    - i. Downloadable form at <http://www.fda.gov/medwatch/getforms.htm>
  - b. UP/SAE Coversheet
    - i. SAE Coversheet is found in [Appendix H-2](#). A modifiable Microsoft Word document is also available from the Data Coordinating Center. An electronic signature on the document will be accepted.
3. Scan and email above documents to [[contact]](mailto:[contact]) with the subject title as "IRB # SAE".
  - a. All SAE reports received at this account are forwarded immediately to study Principal Investigator, and to Coordinating Center personnel.
  - b. While not required, if available and applicable, please also include the local IRB submission for this event in the submission.
4. If an email receipt from Coordinating Center personnel is not received within one working day, please call [contact] and/or email [[contact]](mailto:[contact]).

**14.3.2.3 COH Investigative Sites: Procedure for Reporting SAEs/UPs to the Coordinating Center**

1. Email the following information to [[contact]](mailto:[contact]) and [[contact]](mailto:[contact]):
  - a. Participant ID, date the event met criteria for reporting, whether the event meets the definition of serious, whether the event is an unanticipated problem, grade of event, attribution of event, whether the event is a known expected toxicity to study agent.
2. Complete the iRIS AE/UP reporting form per COH reporting timeline.

**14.3.3 Additional Reporting Requirements of the Study Principal Investigator**

**14.3.3.1 Reporting to COH IRB and DSMC**

The study PI (or designee) will report to COH IRB and DSMC via iRIS all reportable serious adverse events that occur at COH and non-COH sites and meet COH IRB and DSMC expedited reporting criteria according to City of Hope's Institutional policy. The study PI will also submit a Protocol Management Team (PMT) report to the COH DSMC at the frequency outlined in Section 3.6. This report will include a review of aggregate adverse event data.

**14.3.3.2 Reporting to the FDA**

The study PI (or designee) will be responsible for contacting the Office of IND Development and Regulatory Affairs (OIDRA) at COH to ensure prompt reporting of safety reports to the FDA. OIDRA will assist the PI with the preparation of the report and submit the report to the FDA in accordance with the approved City of Hope's Institutional policy.

Serious Adverse Events meeting the requirements for expedited reporting to the Food and Drug Administration (FDA), as defined in [21 CFR 312.32](#), will be reported as an IND safety report using the [MedWatch Form FDA 3500A for Mandatory Reporting](#).

The criteria that require reporting using the Medwatch 3500A are:

- Any unexpected fatal or life threatening adverse experience associated with use of the drug must be reported to the FDA no later than 7 calendar days after initial receipt of the information [[21 CFR 312.32\(c\)\(2\)](#)]
- Any adverse experience associated with use of the drug that is both serious and unexpected must be submitted no later than 15 calendar days after initial receipt of the information [[21 CFR 312.32\(c\)\(1\)](#)]
- Any follow-up information to a study report shall be reported as soon as the relevant information becomes available. [[21 CFR 312.32\(d\)\(3\)](#)]

In addition, the study PI will submit annually within 60 days (via COH OIDRA) of the anniversary date of when the IND went into effect, an annual report to the FDA which is to include a narrative summary and analysis of the information of all FDA reports within the reporting interval, a summary report of adverse drug experiences, and history of actions taken since the last report because of adverse drug experiences.

#### **14.3.3.3 Reporting to Participating Investigators**

The study PI (or designee) will report all reportable serious adverse events to participating investigators as an IND Safety Report occurring within 30 calendar days of receipt of sponsor (lead site) notification, and indicate whether or not a protocol and/or consent form change is required. A cover letter will indicate the protocol title, the IND#, whether the FDA was informed, and, for non-COH sites, a statement that the report should be submitted to their local IRB for review as an IND safety report if applicable per local IRB policy.

The study PI will also forward to participating sites all IND safety reports received from AbbVie, indicating whether a consent form or protocol change is required within 30 days of notification to study PI.

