#### **14.3.3.4 Reporting to AbbVie**

All serious adverse events and AESIs (initial and follow-up information) will be reported by the study PI to AbbVie within 24 hours per the following guidelines: The initial report will be as complete as possible and include an assessment of the causal relationship between the event and the study agent(s). Information not available at the time of the initial report will be documented on a follow-up report and submitted to AbbVie. The principal Investigator shall make available to AbbVie promptly such records as may be necessary and pertinent to investigate any such event, if specifically requested by AbbVie. In addition, report to AbbVie all non-serious adverse events of tumor lysis syndrome (TLS).

- Copy AbbVie on the submission to the FDA of events meeting the definition of IND safety reports at the time of submission to the Agency.
- Notify AbbVie upon any subjects receiving venetoclax whose pregnancy has resulted in a negative outcome or untoward event during the course of pregnancy or upon delivery.

The AbbVie tracking number (**Study # 11354**) will be included on expedited reports (or on the fax cover letter). A copy of the fax transmission confirmation of the expedited report to AbbVie will be retained with the patient records.

AbbVie's contact for reporting serious adverse drug experiences, pregnancy experiences, non-serious adverse events of tumor lysis syndrome, and communication of FDA submissions of IND safety reports is:

E-mail: [[contact]](mailto:[contact])

- Submit annually within 60 days (via COH OIDRA) of the anniversary date of when the IND went into effect, an annual report to the FDA which is to include a narrative summary and analysis of the information of all FDA reports within the reporting interval, a summary report adverse drug experiences, history of actions taken since the last report because of adverse drug experiences.
- Report every 3 months to the COH DSMC a Protocol Management Team (PMT) report, to include aggregate analysis of safety information and accrual and participant status.
- Circulate to all participating sites for submission to their IRBs the COH DSMC report and DSMC recommendation, in accordance with NIH guidance.
- Report to AbbVie aggregate safety information every 3 months at time of COH PMT report.

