- Forward to participating sites all reportable AE/UPs as an IND Safety Report occurring within 30 calendar days of receipt of lead site notification, and indicate whether or not a protocol and/or consent form change is required. A cover letter will indicate the protocol title, the IND#, whether

the FDA was informed, and, for non-COH sites, a statement that the report should be submitted to their local IRB for review as an IND safety report if applicable per local IRB policy.

- Forward to participating sites all safety reports received from AbbVie for venetoclax that have not occurred directly on this protocol, indicating whether a consent form or protocol change is required within 30 days of notification to Study PI.

**Product Complaints:** In addition to compliance with all FDA requirements pursuant to 21 CFR 211 and 21 CFR 820, Principal Investigator will report to AbbVie within 24 hours any suspected quality defect in an AbbVie Product or its AbbVie-provided packaging, labeling, or medical device component (collectively, "Product Complaint"). Principal Investigator will report Product Complaints that involve an AbbVie Product, whether AbbVie has supplied the AbbVie Product used in the Study or not. AbbVie's contact for reporting Product Complaints is:

[RD\\_PQC\\[contact]](mailto:[contact])

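### For events filed with the FDA as IND safety reports, investigators at other sites may be told 15 to 23 days after the FDA deadline

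*Combined protocol and SAP*

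**What the plan says.** Four reporting legs are described in Section 14.3.

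- **Site to centre.** Under 14.3.2.1, serious events that meet the criteria "will be reported to the Coordinating Center within 24 hours of notification that the event occurred". For non-COH sites, 14.3.2.2 adds: "All SAE reports received at this account are forwarded immediately to study Principal Investigator, and to Coordinating Center personnel". Other sites are not on that distribution.
- **Centre to FDA.** Under 14.3.3.2, an unexpected fatal or life-threatening experience associated with the drug "must be reported to the FDA no later than 7 calendar days after initial receipt of the information". One that is "both serious and unexpected must be submitted no later than 15 calendar days after initial receipt of the information" is on the longer clock. Both are filed as IND safety reports.
- **Centre to supplier.** Under 14.3.3.4, serious events and AESIs "will be reported by the study PI to AbbVie within 24 hours". The IND safety report itself follows on the FDA clock: "Copy AbbVie on the submission to the FDA of events meeting the definition of IND safety reports at the time of submission".
- **Centre to participating investigators.** Under 14.3.3.3, the study PI is to "report all reportable serious adverse events to participating investigators as an IND Safety Report occurring within 30 calendar days of receipt of sponsor" (lead-site) notification. The bullet list at the end of 14.3.3.4 says much the same: "Forward to participating sites all reportable AE/UPs as an IND Safety Report occurring within 30 calendar days of receipt of lead site notification". The cover letter must state whether the FDA was informed and whether the protocol or consent form must change.

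No section sets a shorter limit for telling the other sites.

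**The concern.** The plan uses one term, IND safety report, for a document with two different deadlines. The 30-day stream plainly includes events already filed with the FDA, because its cover letter must say whether the FDA was informed. For exactly those events, the text allows the regulator and the supplier to hold the report while clinicians giving the same combination at other sites do not.

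What is at stake is the safety of patients already on treatment elsewhere, and of those about to consent there. The protocol/consent-change decision, and any local IRB submission at a non-COH site, also travel with this report and can be late with it.

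**Working it through.** The 30-day limit is a stated rule, so there is no calculated figure to reproduce. The check compares the clocks and then sizes the exposure.

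**Inputs.** Investigator limit 30 days (14.3.3.3, 14.3.3.4). FDA limits 7 and 15 days (14.3.3.2). Cycle length 28 days (5.2). Romidepsin on Days 1, 8 and 15 of each cycle (5.3). Accrual 1-2 patients per month across all sites (12.2). PMT recommended to meet at least monthly (16.3). Assumptions: a month is 30.4 days; one other site has 1/3 to 1/2 of accrual; the FDA and investigator clocks start on the same day.

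**1. Gap between the deadlines**

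- Unexpected fatal or life-threatening: 30 − 7 = 23 days after the FDA deadline.
- Other serious unexpected: 30 − 15 = 15 days after it.
- Against the cycle: 30 − 28 = 2 days longer than Cycle 1.
- From the reporting site's own awareness: up to 1 + 30 = 31 days.

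**2. Position of one patient.** Take a patient at another site whose Day 1 is the day the lead site is notified. A limit of L days falls due on study day L + 1.

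| Limit | Due on | Romidepsin infusions scheduled before that day |
|---|---|---|
| 7 days | Day 8 | 1 (second due that day) |
| 15 days | Day 16 | 3 |
| 30 days | Day 31 | 4 (Days 1, 8, 15 and Cycle 2 Day 1) |

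The 7-day clock gives notice within the first part of Cycle 1. The 15-day clock would not come before this patient's Cycle 1 infusions, but it would come before Cycle 2.

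**3. New starts at one other site.** Expected starts m = (patients per month) × share × L / 30.4.

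- L = 30: from 1 × 1/3 × 30/30.4 = 0.33 to 2 × 1/2 × 30/30.4 = 0.99.
- L = 15: 0.16 to 0.49.
- L = 7: 0.08 to 0.23.

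With Poisson arrivals, the chance of at least one start in 30 days is 1 − exp(−m): 28%-48% at a one-third share and 39%-63% at one half.

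**4. Whether PMT meetings close the gap.** If meetings are monthly and the event falls at random between them, the chance that the next meeting is more than w days away is 1 − w/30.4. This is 77% for w = 7, 51% for w = 15 and 8% for w = 28. A monthly meeting would usually bring news before Day 30, but often after the FDA deadline.

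**The case against.** The case against has substance.

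- **Scope.** The 30-day clause covers all reportable serious events, including expected and unrelated ones. The 7- and 15-day clocks cover only unexpected events associated with the drug. This stands, and it confines the conflict to that subset.
- **Other controls.** Site investigators belong to the PMT, which is responsible for ongoing safety monitoring (16.3). Every enrolment is slotted and registered centrally (4.2-4.4) by a centre that already knows of the event. Accrual is suspended at two or more unacceptable toxicities in the lead-in (12.1.1) and on the TLS rules (12.4). The lead-in also starts with only three evaluable patients before their assessment. These points stand as mitigation, chiefly for new starts. However, the PMT meeting frequency is only recommended, and neither registration nor suspension sets a time for telling an investigator with patients already on treatment.

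A reader might also infer four stronger things that the documents do not support.

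- *The supplier has the same report in 24 hours.* It has the serious-event report by then; the IND safety report is copied to it at FDA submission.
- *The exposure is the early TLS window.* TLS is a listed toxicity of both drugs (6.1.1, 6.1.2), so under 14.2.3 it would generally be expected and outside the FDA clocks. It also has its own accrual rule.
- *The lead-in's validity is affected.* Tolerability rests on counts of unacceptable toxicity (12.1.1), which do not depend on when another site receives a letter.
- *One to two patients start uninformed.* That rate is for all sites, including the site of the event and the lead site.

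**Conclusion.** The concern holds for serious, unexpected, drug-associated events. For these, the plan permits participating investigators to receive the IND safety report up to 23 days (fatal or life-threatening) or 15 days (other) after the FDA deadline, with a limit longer than one treatment cycle. About 0.3-1 new patients would start at one other site in that time, on the assumed share of accrual.

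The conclusion rests on reading the loosely worded 30 days as a deadline for sending the report, and on the FDA and investigator clocks starting together. Thirty days is a worst case under these clauses; it should not be read as saying that sites will be uninformed for a whole cycle. What the cited federal regulation requires for notifying investigators is not reproduced in the documents, and nothing here depends on it.

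The text above says other sites, without a number, because the synopsis lists two sites and Section 12.2 says three. Those should be reconciled too.

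**What to change.** Reconcile 14.3.3.2, 14.3.3.3 and the matching bullet in 14.3.3.4:

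- Any event filed with the FDA as an IND safety report goes to all participating investigators no later than the FDA submission. That is at most 7 calendar days after initial receipt for unexpected fatal or life-threatening events, and at most 15 for other serious unexpected events.
- The 30-day limit from lead-site notification stays only for reportable events that need no expedited FDA report.
- The 30 days should be attached clearly to sending the report.

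The cost is about two sentences in the next amendment. The report exists at FDA submission and the supplier is already copied then, so the added work is adding the sites to that distribution. One trade-off is that the decision on a protocol or consent change may not be ready by day 7 or 15. The clause should let it follow in a later communication so that it does not hold up the notice.

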#### **14.3.3.4 Reporting to AbbVie**

All serious adverse events and AESIs (initial and follow-up information) will be reported by the study PI to AbbVie within 24 hours per the following guidelines: The initial report will be as complete as possible and include an assessment of the causal relationship between the event and the study agent(s). Information not available at the time of the initial report will be documented on a follow-up report and submitted to AbbVie. The principal Investigator shall make available to AbbVie promptly such records as may be necessary and pertinent to investigate any such event, if specifically requested by AbbVie. In addition, report to AbbVie all non-serious adverse events of tumor lysis syndrome (TLS).

- Copy AbbVie on the submission to the FDA of events meeting the definition of IND safety reports at the time of submission to the Agency.
- Notify AbbVie upon any subjects receiving venetoclax whose pregnancy has resulted in a negative outcome or untoward event during the course of pregnancy or upon delivery.

The AbbVie tracking number (**Study # 11354**) will be included on expedited reports (or on the fax cover letter). A copy of the fax transmission confirmation of the expedited report to AbbVie will be retained with the patient records.

AbbVie's contact for reporting serious adverse drug experiences, pregnancy experiences, non-serious adverse events of tumor lysis syndrome, and communication of FDA submissions of IND safety reports is:

E-mail: [[contact]](mailto:[contact])

- Submit annually within 60 days (via COH OIDRA) of the anniversary date of when the IND went into effect, an annual report to the FDA which is to include a narrative summary and analysis of the information of all FDA reports within the reporting interval, a summary report adverse drug experiences, history of actions taken since the last report because of adverse drug experiences.
- Report every 3 months to the COH DSMC a Protocol Management Team (PMT) report, to include aggregate analysis of safety information and accrual and participant status.
- Circulate to all participating sites for submission to their IRBs the COH DSMC report and DSMC recommendation, in accordance with NIH guidance.
- Report to AbbVie aggregate safety information every 3 months at time of COH PMT report.
- Forward to participating sites all reportable AE/UPs as an IND Safety Report occurring within 30 calendar days of receipt of lead site notification, and indicate whether or not a protocol and/or consent form change is required. A cover letter will indicate the protocol title, the IND#, whether

the FDA was informed, and, for non-COH sites, a statement that the report should be submitted to their local IRB for review as an IND safety report if applicable per local IRB policy.

- Forward to participating sites all safety reports received from AbbVie for venetoclax that have not occurred directly on this protocol, indicating whether a consent form or protocol change is required within 30 days of notification to Study PI.

**Product Complaints:** In addition to compliance with all FDA requirements pursuant to 21 CFR 211 and 21 CFR 820, Principal Investigator will report to AbbVie within 24 hours any suspected quality defect in an AbbVie Product or its AbbVie-provided packaging, labeling, or medical device component (collectively, "Product Complaint"). Principal Investigator will report Product Complaints that involve an AbbVie Product, whether AbbVie has supplied the AbbVie Product used in the Study or not. AbbVie's contact for reporting Product Complaints is:

[RD\\_PQC\\[contact]](mailto:[contact])

